## 5.2 Trial Treatments

The treatment to be used in this trial is outlined below in Table 2

Table 2 Trial Treatment

Drug	Dose/Potency	Dose Frequency	Route of Administration	Regimen/Treatment Period	Use
Pembrolizumab	200 mg	Q3Wa	IV infusion	Day 1 of each 3 week cycle	Experimental
External Beam Radiation Therapy	20-50 Gy in $\leq$ 3 Gy fractions	Daily	External Beam	5 days per week consecutively until treatment is complete (not including holidays and weekends)	Standard of Care

bThe MK-3475 dosing interval may be modified secondary to toxicity as described in Section 5.2.1.2

Trial treatment should begin on the day of randomization or as close as possible to the date on which treatment is allocated/assigned.

### 5.2.1 Dose Selection/Modification

#### 5.2.1.1 Dose Selection

The rationale for selection of doses to be used in this trial is provided in Section 4.0 – Background and Rationale. Details on preparation and administration of pembrolizumab (MK-3475) are provided in the Pharmacy Manual.

Radiation will be given as per our institutional standard for NHL. Fractionation schedules include 40-50 Gy in 3 Gy fractions or less, which are acceptable doses for salvage RT for patients with aggressive NHL. Hypofractionated radiation therapy when given to patients with progressive disease will be given at fraction sizes of at least 4 Gy per fractions. All radiation therapy will be administered daily (likely excluding weekends and holidays when applicable). All radiation therapy will be standard of care.

#### 5.2.1.2 Dose Modification (Escalation/Titration/Other)

Adverse events (both non-serious and serious) associated with pembrolizumab exposure may represent an immunologic etiology. These adverse events may occur shortly after the first dose or several months after the last dose of treatment. Pembrolizumab must be withheld for drug-related toxicities and severe or life-threatening AEs as per 3 below. See Section 5.6 for supportive care guidelines, including use of corticosteroids.

**Table 3 Dose modification and toxicity management guidelines for immune-related AEs associated with pembrolizumab**

General instructions:				
Immune-related AEs	Toxicity grade or conditions (CTCAEv4.0)	Action taken to pembrolizumab	irAE management with corticosteroid and/or other therapies	Monitor and follow-up
Pneumonitis	Grade 2	Withhold	
 
Administer corticosteroids (initial dose of 1-2 mg/kg prednisone or equivalent) followed by taper
 
	
 
Monitor participants for signs and symptoms of pneumonitis
 
Evaluate participants with suspected pneumonitis with radiographic imaging and initiate corticosteroid treatment
 
Add prophylactic antibiotics for opportunistic infections
 

	Grade 3 or 4, or recurrent Grade 2	Permanently discontinue		
Diarrhea / Colitis	Grade 2 or 3	Withhold	
 
Administer corticosteroids (initial dose of 1-2 mg/kg prednisone or equivalent) followed by taper
 
	
 
Monitor participants for signs and symptoms of enterocolitis (ie, diarrhea, abdominal pain, blood or mucus in stool with or without fever) and of bowel perforation (ie, peritoneal signs and ileus).
 
Participants with <math>\geq</math> Grade 2 diarrhea suspecting colitis should consider GI consultation and performing endoscopy to rule out colitis.
 
Participants with diarrhea/colitis should be advised to drink liberal quantities of clear fluids. If sufficient oral fluid intake is not feasible, fluid and electrolytes should be substituted via IV infusion.
 

	Grade 4	Permanently discontinue		

AST / ALT elevation or Increased bilirubin	Grade 2	Withhold	
 
Administer corticosteroids (initial dose of 0.5- 1 mg/kg prednisone or equivalent) followed by taper
 
	
 
Monitor with liver function tests (consider weekly or more frequently until liver enzyme value returned to baseline or is stable)
 

	Grade 3 or 4	Permanently discontinue	
 
Administer corticosteroids (initial dose of 1-2 mg/kg prednisone or equivalent) followed by taper
 
	
Type 1 diabetes mellitus (T1DM) or Hyperglycemia	Newly onset T1DM or Grade 3 or 4 hyperglycemia associated with evidence of $\beta$ -cell failure	Withhold	
 
Initiate insulin replacement therapy for participants with T1DM
 
Administer anti-hyperglycemic in participants with hyperglycemia
 
	
 
Monitor participants for hyperglycemia or other signs and symptoms of diabetes.
 

Hypophysitis	Grade 2	Withhold	
 
Administer corticosteroids and initiate hormonal replacements as clinically indicated.
 
	
 
Monitor for signs and symptoms of hypophysitis (including hypopituitarism and adrenal insufficiency)
 

	Grade 3 or 4	Withhold or permanently discontinue 		
Hyperthyroidism	Grade 2	Continue	
 
Treat with non-selective beta-blockers (eg, propranolol) or thionamides as appropriate
 
	
 
Monitor for signs and symptoms of thyroid disorders.
 

	Grade 3 or 4	Withhold or permanently discontinue 		
Hypothyroidism	Grade 2-4	Continue	
 
Initiate thyroid replacement hormones (eg, levothyroxine or liothyroinine) per standard of care
 
	
 
Monitor for signs and symptoms of thyroid disorders.
 

Nephritis and Renal dysfunction	Grade 2	Withhold	
 
Administer corticosteroids (prednisone 1-2 mg/kg or equivalent) followed by taper.
 
	
 
Monitor changes of renal function
 

	Grade 3 or 4	Permanently discontinue		
Myocarditis	Grade 1 or 2	Withhold	
 
Based on severity of AE administer corticosteroids
 
	
 
Ensure adequate evaluation to confirm etiology and/or exclude other causes
 

	Grade 3 or 4	Permanently discontinue		

All other immune-related AEs	Intolerable/persistent Grade 2	Withhold	

Based on type and severity of AE administer corticosteroids

Ensure adequate evaluation to confirm etiology and/or exclude other causes

	Grade 3	Withhold or discontinue based on the type of event. Events that require discontinuation include and not limited to: Gullain-Barre Syndrome, encephalitis	
	Grade 4 or recurrent Grade 3	Permanently discontinue	

1. Withhold or permanently discontinue pembrolizumab is at the discretion of the investigator or treating physician.

**NOTE:**  
For participants with Grade 3 or 4 immune-related endocrinopathy where withhold of pembrolizumab is required, pembrolizumab may be resumed when AE resolves to  $\leq$  Grade 2 and is controlled with hormonal replacement therapy or achieved metabolic control (in case of T1DM).

Dosing interruptions are permitted in the case of medical / surgical events or logistical reasons not related to study therapy (e.g., elective surgery, unrelated medical events, patient vacation, and/or holidays). Subjects should be placed back on study therapy within 3 weeks of the scheduled interruption, unless otherwise discussed with the Sponsor. The reason for interruption should be documented in the patient's study record.

### **5.2.3 Trial Blinding/Masking**

This is an open-label trial; therefore, the Sponsor, investigator and subject will know the treatment administered.

### **5.3 Randomization or Treatment Allocation**

This is an unblinded, non-randomized trial among patients with relapsed and refractory aggressive NHL. Trial enrollees will receive MK-3475 concurrent with fractionated EBRT. Patients will be stratified according to extent of disease included in the radiation therapy field(s) as follows:

- 1) Cohort 1: Relapsed/Refractory Aggressive B-cell lymphoma with disease excluded from the Radiation Therapy Field (n=20)
- 2) Cohort 2: Relapsed/Refractory Aggressive B-cell lymphoma with all sites of radiographically evident disease treated in 1-2 radiation therapy field(s). Disease (n=20)

### **5.4 Radiation Therapy**

Radiation treatment will consist of definitive radiation therapy to a site of relapsed/refractory disease encompassed in one radiation therapy plan. Patients in Cohort 1 with relapsed or refractory lymphoma will be treated to one to two region(s) of disease with at least one distinct lesion excluded from the field and designated the “unirradiated lesion”. Patients in Cohort 2 with relapsed or refractory lymphoma will be treated with one to two RT plan(s) encompassing all sites of evident active disease. All patients (in both cohorts) will receive EBRT to a dose of 40-50 Gy in fractions sizes of 3 Gy or less. Integrated boost technique is permitted. Treatment will be administered 5 days per week, excluding holidays and weekends. For patients that are eligible for salvage hypo-fractionated EBRT, fraction sizes of at least 4 Gy will be used with a conformal delivery approach.

#### **Radiation Simulation**

CT based simulation and RT planning is required for every patient. Simulation will be performed roughly one week prior to initiation of therapy. Custom immobilization should be used when appropriate. During simulation, patients will be evaluated for respiration induced motion of the target volume. Based on this evaluation, a 4D CT simulation or breath-hold may be used for motion management. The CT simulation images will be transferred over to the treatment planning system (Pinnacle or Eclipse) for radiation therapy planning.

#### **Radiation Technique**

The radiation technique utilized is at the discretion of the treating radiation oncologist and will be standard of care and institutional standards. Priority to sparing normal tissue should be maintained at all times. Potential treatment modalities include 3D conformal RT, Intensity Modulated Radiation Therapy (IMRT), Volumetric Arc Therapy (VMAT), Proton radiotherapy and Electron radiotherapy. Utilization of daily image guidance is at the discretion of the treating radiation oncologist with the goal of limiting set up uncertainty to less than 10 mm variation. Integrated boost technique is permitted at fractions of 3 Gy or less.

#### **Radiation Target Volumes and Dosimetry**

- 1) Gross tumor volume (GTV) is defined as the tumor bulk visible radiographically on the CT planning scan.

2) The Clinical Target Volume (CTV) and Planning Target Volume (PTV) will be 5 -15 mm based on the type of image guidance utilized and the planned radiation technique. The prescription isodose line should cover greater than 98% of the GTV. We recommend PTV coverage of >95% when possible.

For patients enrolled in Cohort 1, the lesion(s) designated as the non-index lesion(s) outside of the radiation field should be at least 5 cm away from the radiation field. This lesion should be identified and documented prior to initiation of protocol therapy. In cases where the lesion is within 5 cm of the field, the non-index lesion(s) should be contoured and should receive a dose no greater than 5 Gy over the course of the entire radiation treatment.

## **Dose Constraints**

Dose constraints are according to QUANTEC as well as institutional dose constraint guidelines established by the Department of Radiation Oncology Hematologic Malignancy Section . Important dose restraints include:

- 1) Spinal cord Max point dose <45 Gy
- 2) Lung: Mean lung dose (MLD)  $\leq$ 13.5 Gy, V20 < 30%, V15<35%, V10 <40% and V55<55% .
- 3) Heart: Mean <15 Gy
- 4) Brachial Plexus: Maximum dose <66 Gy
- 5) Parotid gland: Mean <26 Gy
- 6) Submandibular gland: Mean <26 Gy
- 7) Small Bowel: 1cc <55 Gy 
- 8) Kidney: Mean <13 Gy, V20 < 33% for at least one kidney
- 9) Liver: Mean <28 Gy, V30 < 30% and V20 <50%
- 10) Bone marrow: pelvic bone marrow V10 <95% and V20 <76% 

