#### 5.1.2 Subject Inclusion Criteria

In order to be eligible for participation in this trial, the subject must:

1. Have at least one site of lymphomatous disease amenable to external beam radiation therapy (EBRT)
2. Have pathologic confirmation of aggressive Non-Hodgkin Lymphoma (including diffuse large B cell lymphoma, transformed follicular lymphoma, transformed marginal zone lymphoma, primary mediastinal B-cell lymphoma, T cell lymphoma and NK T-cell lymphoma). Patients with indolent B cell lymphoma are excluded.
3. Be willing and able to provide written informed consent/assent for the trial.
4. Be  $\geq 18$  years of age on day of signing informed consent.
5. Have measurable disease ( $\geq 1.5$  cm in the longest diameter for nodal or extranodal disease)
6. Have provided archival tumor tissue sample or newly obtained core or excisional biopsy of a tumor lesion not previously irradiated. Formalin-fixed, paraffin embedded (FFPE) tissue blocks are preferred to slides. *Newly obtained* biopsies are preferred to *archived* tissue. *Newly-obtained is defined as a specimen obtained up to 6 weeks (42 days) prior to initiation of treatment on Day 1. Subjects for whom newly-obtained samples cannot be provided (e.g. inaccessible or subject safety concern) may submit an archived specimen.* Note: If submitting unstained cut slides, newly cut slides should be submitted to the testing laboratory within 14 days from the date slides are cut.
7. Have an Eastern Cooperative Oncology Group (ECOG) performance status of 0 to 1. Evaluation of ECOG is to be performed within 7 days prior to the date of allocation/randomization.
8. Demonstrate adequate organ function as defined in Table 1, all screening labs should be performed within 10 days of treatment initiation.

Table 1 Adequate Organ Function Laboratory Values

System	Laboratory Value
--------	------------------

Hematological	
Absolute neutrophil count (ANC)	$\geq 1,000 / \text{mcL}$
Platelets	$\geq 50,000 / \text{mcL}$
Hemoglobin	$\geq 8 \text{ g/dL}$ or $\geq 5.6 \text{ mmol/L}$ without transfusion or EPO dependency (within 7 days of assessment)
Renal	
Serum creatinine OR Measured or calculated a creatinine clearance (GFR can also be used in place of creatinine or CrCl)	$\leq 1.5 \times \text{upper limit of normal (ULN)}$ OR $\geq 60 \text{ mL/min}$ for subject with creatinine levels $> 1.5 \times$ institutional ULN
Hepatic	

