### **7.1.4.2 Treatment Period**

#### **7.1.4.2.1 Salvage Hypo-Fractionated Radiation Therapy**

Patients that receive initial therapy with MK-3475 and fractionated EBRT that develop progressive disease (PD) in any of the follow up evaluations may be considered for salvage EBRT. Patients will be scheduled for simulation and will initiate salvage radiation therapy as soon as possible (usually within 1 week). EBRT will be given concurrently with remaining cycles of MK-3475 with a fraction size of at least 4 Gy (hypo-fractionated approach). The final dose will be determined by the treating radiation oncologist according based on disease histology.

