**AND**

- Experienced an investigator-determined confirmed radiographic disease progression after stopping their initial treatment with pembrolizumab
- Did not receive any anti-cancer treatment since the last dose of pembrolizumab
- Has a performance status of 0 or 1 on the ECOG Performance Scale
- Demonstrates adequate organ function as detailed in Section 5.1.2
- Female subject of childbearing potential should have a negative serum or urine pregnancy test within 72 hours prior to receiving retreatment with study medication.
- Female subject of childbearing potential should be willing to use 2 methods of birth control or be surgically sterile, or abstain from heterosexual activity for the course of the study through 120 days after the last dose of study medication (Reference Section 5.7.2). Subjects of child bearing potential are those who have not been surgically sterilized or have been free from menses for > 1 year.
- Male subject should agree to use an adequate method of contraception starting with the first dose of study therapy through 120 days after the last dose of study therapy.
- Does not have a history or current evidence of any condition, therapy, or laboratory abnormality that might interfere with the subject's participation for the full duration of the trial or is not in the best interest of the subject to participate, in the opinion of the treating investigator.

Subjects who restart treatment will be retreated at the same dose and dose interval as when they last received pembrolizumab. Treatment will be administered for up to one additional year.

Visit requirements are outlined in Section 6.0 – Trial Flow Chart.

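### Two printed limits have no effect as written: lung V55 below 55% in the dose constraints, and albumin of at least 2.5 mg/dL in the eligibility table

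*Combined protocol and SAP*

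**What the plan says.** **Lung.** Dose Constraints, within Section 5.4, defers to QUANTEC and to institutional guidelines and then names the constraints it regards as important. The lung entry opens with "Lung: Mean lung dose (MLD"), capped at 13.5 Gy, and continues with four dose-volume limits: "V20 < 30%, V15<35%, V10 <40% and V55<55", the last figure being a percentage like the others. On prescribed dose, Section 5.4 says "All patients (in both cohorts) will receive EBRT to a dose of 40-50 Gy in fractions sizes of 3 Gy or less". For salvage treatment after progression, Section 7.1.4.2.1 sets a minimum fraction size but prints no ceiling on total dose: "The final dose will be determined by the treating radiation oncologist".

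**Albumin.** Inclusion criterion 8 in Section 5.1.2 reads "Demonstrate adequate organ function as defined in Table 1". The albumin row of that table gives a floor of 2.5 mg/dL. The haemoglobin row of the same table is in g/dL. For the Second Course Phase, Section 7.1.4.5 lists among its conditions "Demonstrates adequate organ function as detailed in Section 5.1.2", so the same albumin floor governs retreatment.

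No other part of the document gives a different albumin limit or a further lung limit that would correct either figure.

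**The concern.** Both figures are in operative text: one is a radiation planning limit, the other an entry criterion. A limit that no plan or patient can fail gives no protection, and each of these looks like a slip.

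In the lung list the doses fall (20, 15, 10 Gy) while the permitted volumes rise (30, 35, 40%). A fourth entry with a 55% volume should continue to a dose below 10 Gy, but it jumps to 55 Gy. If a low-dose limit was intended, the printed list has none. That is relevant in a trial that can give thoracic radiation with pembrolizumab. Section 5.6.1 suspends chest radiation for pneumonitis of Grade 2 or higher, and the dose-modification table stops pembrolizumab permanently for Grade 3 or 4.

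For albumin, a site that follows the text literally screens nobody out. A site that silently reads g/dL applies a criterion different from the written one.

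**Working it through.** The plan derives neither figure, so there is no calculation of its own to reproduce. The check asks whether each limit can ever bind.

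**Lung inputs (Section 5.4, Dose Constraints):** mean lung dose at most 13.5 Gy; V20 < 30%; V15 < 35%; V10 < 40%; V55 < 55%. Vx is the percentage of lung receiving at least x Gy.

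1. *Ordering.* Vx cannot rise as x rises, so V55 ≤ V20 < 30%. This alone makes a 55% cap at 55 Gy redundant.
2. *Mean dose.* Lung receiving at least 55 Gy contributes at least 55 × V55 to the mean. Hence V55 ≤ 13.5/55 = 0.2455, or 24.5%.
3. *Joint check.* A linear program over lung dose distributions from 0 to 80 Gy, under the other four limits, maximises Vx at several doses:

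| Dose x (Gy) | Largest Vx allowed by the other four limits |
|---|---|
| 55 | 24.5% |
| 50 | 27.0% |
| 20 | 30% |
| 15 | 35% |
| 10 | 40% |
| 3, 5, 7, 9, 9.9 | 100% |

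4. *Where a 55% cap could bind.* At 10 Gy and above, Vx is already held to 40% or less. A 55% cap can therefore bind only below 10 Gy, where the other four limits allow up to 100%. For example, the whole lung at 9.9 Gy has a mean of 9.9 Gy and V10 = 0.
5. *Dependence on prescribed dose.* Steps 1 and 2 do not use the prescription, so they also cover salvage radiation with no stated ceiling. At the protocol dose, any lung volume at 55 Gy would need a hot spot of 55/50 = 110% of a 50 Gy prescription, or 55/40 = 137.5% of 40 Gy.
6. *What the printed limits permit.* Take 29% of lung at 25 Gy and 71% at 6 Gy. The mean is 0.29 × 25 + 0.71 × 6 = 7.25 + 4.26 = 11.51 Gy. V20 = V15 = V10 = 29%, V55 = 0 and V5 = 100%. All five printed limits are met. This is an arithmetic illustration, not a predicted treatment plan.

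**Albumin inputs:** the printed floor of 2.5 mg/dL (Section 5.1.2, Table 1), and an assumed patient range for serum albumin of about 1 to 5 g/dL, which is not in the documents.

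1. 2.5 mg/dL ÷ 1000 = 0.0025 g/dL.
2. The assumed range is 1000 to 5000 mg/dL. The ratios to the printed floor are 1000/2.5 = 400 and 5000/2.5 = 2000.
3. Read as 2.5 g/dL (2500 mg/dL), the floor falls inside the assumed range and can exclude patients.

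**The case against.** The arithmetic is not in dispute. The case on the other side concerns materiality and what was intended.

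- *The printed list is not the whole standard.* QUANTEC and the institutional guidelines also govern, and Section 5.4 gives priority to sparing normal tissue. This stands. The guidelines are not reproduced, so one cannot say that low-dose lung volume is unconstrained in practice, only that the printed limits do not constrain it beyond what the mean dose does.
- *A redundant limit is harmless and need not be an error.* Redundancy alone would not prove a misprint. The falling doses beside rising volumes make one likely.
- *The volume, not the dose, could be the misprint.* A V55 cap below 24.5% could bind. The sequence favours a dose error but does not prove it, so the source must be checked before anything is changed.
- *The text was read from PDF, so an extraction slip in the lung entry cannot be fully excluded.* The entry is legible and nothing else contradicts it. The source file settles this.
- *Nobody would screen against 0.0025 g/dL.* That is probably right, since haemoglobin in the same table is in g/dL. It limits the consequence but does not make the written criterion correct.

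**Conclusion.** Both limits are wrong as written, and the point is minor. The lung result follows from the limits on that line alone: V55 is held below 30% by V20 and to at most 24.5% by the mean dose, so a 55% cap never binds at any prescribed dose. That V5 was meant is an inference from the order of the list. The albumin result rests on the assumed range of 1 to 5 g/dL and holds across all of it; the printed floor excludes nobody at entry or at retreatment. The likely practical effect is small: four other lung limits, the external guidelines and the remaining organ-function criteria stay active. Nothing follows for sample size, stopping boundaries or the analyses.

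**What to change.** In Dose Constraints (Section 5.4), check the fifth lung parameter against the reference cited on that line or the institutional guideline, and print the confirmed value. The list points to a dose below 10 Gy; use V5 < 55% only if the source says so. In Table 1 of Section 5.1.2, change the albumin unit so that the floor is 2.5 g/dL. Section 7.1.4.5 refers back to Section 5.1.2, so retreatment eligibility is corrected by the same edit.

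The cost is one parameter and one unit in the next amendment, with no change to design, sample size or analysis.

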## **5.5 Concomitant Medications/Vaccinations (allowed & prohibited)**

Medications or vaccinations specifically prohibited in the exclusion criteria are not allowed during the ongoing trial. If there is a clinical indication for one of these or other medications or vaccinations specifically prohibited during the trial, discontinuation from trial therapy or vaccination may be required. The investigator should discuss any questions regarding this with the Merck Clinical team. The final decision on any supportive therapy or vaccination rests with the investigator and/or the subject's primary physician.

### **5.5.1 Acceptable Concomitant Medications**

All treatments that the investigator considers necessary for a subject's welfare may be administered at the discretion of the investigator in keeping with the community standards of medical care. All concomitant medication will be recorded on the case report form (CRF) including all prescription, over-the-counter (OTC), herbal supplements, and IV medications and fluids. If changes occur during the trial period, documentation of drug dosage, frequency, route, and date may also be included on the CRF.

All concomitant medications received within 28 days before the first dose of trial treatment and 30 days after the last dose of trial treatment should be recorded. Concomitant medications administered after 30 days after the last dose of trial treatment should be recorded for SAEs and ECIs as defined in Section 7.2.

